### **5.2.1. Analysis Populations**

**Enrolled population:** The enrolled population is defined as all participants who sign informed consent.

**Intent-to-treat (ITT) population:** The ITT population analysis set is defined as all randomized patients, even if the patient does not take the assigned treatment, does not receive the correct treatment, or otherwise does not follow the protocol.

**Per-Protocol (PPS) population:** The PPS populations is defined as all randomized patients who do not commit an Important Protocol Deviation (IPD) that could potentially compromise efficacy results.

**Safety population:** The safety population is defined as all randomized patients who receive at least 1 dose of their assigned double-blind study treatment..

**Maintenance Period Population:** All ITT patients who received at least one dose of study treatment and have entered the maintenance period at Week 16 (Visit 8).

Unless otherwise specified, the efficacy and health outcome analyses will be conducted on the ITT population (Gillings and Koch 1991), which seeks to preserve the benefits of randomization and avoid the issue of selection bias. Patients will be analyzed according to the treatment to which they were randomized.

Safety analyses will be done on the safety population. Patients will be analyzed according to the dosing regimen to which they were assigned. Analyses of the safety endpoints, many of which are incidence based, will include all patients in the safety population, unless specifically stated otherwise.

In the rare situation where a patient is Lost to Follow-up at the first postbaseline visit, but some safety data exists (eg, unscheduled laboratory assessments) after first dose of study drug, a listing of the data or a patient profile will be provided.

### **5.2.2. Definition of Baseline and Postbaseline Measures**

The baseline value for the efficacy and health outcomes for the Induction and Maintenance Periods is defined as the last non-missing measurement on or prior to the date of first study drug administration (expected at Week 0, Visit 2). The baseline value for the daily diary assessments (Itch NRS, Skin Pain NRS) is defined as the average of the non-missing assessments in the last 7 days prior to the date of first study drug administration (expected at Week 0, Visit 2). Criteria for derivation of the weekly average requires that there must be at least 4 non-missing measurements in the 7 days indicated, otherwise, an expanded window of 14 days prior to first study drug administration, if available, may be utilized in order to obtain the most recent 4 non-missing measurements prior to first study drug administration (ie, Day -14 to Day -1). If there are not at least 4 non-missing assessments collected prior to the date of first study drug

administration using the aforementioned method, then the baseline will be designated as missing. Other definitions of baseline value, such as the last measurement on or prior to rescue, may be used to conduct additional supporting analyses.

Postbaseline measurements are collected after study drug administration through Week 60 (Visit 801) or early discontinuation visit. For data collected in the electronic Clinical Outcomes Assessment (eCOA) tablet (including Patient-Reported Outcomes [PRO] and Clinician-Reported Outcomes [ClinRO]) and related to efficacy assessments, unscheduled postbaseline visits that fall within the visit windows defined by Lilly will be summarized in the by-visit analyses if there is no scheduled visit available. That is, a  $\pm 2$  day window is applied to Visit 3 (Week 1), Visit 4 (Week 2), and Visit 5 (Week 4), and a  $\pm 4$  day window is applied to Visit 6 (Week 8), Visit 7 (Week 12), and Visit 8 (Week 16), as well as to every visit in the Maintenance Period. If there is more than 1 unscheduled visit within the defined visit window and no scheduled visit is available, the unscheduled visit closest to the scheduled visit date will be used.

Postbaseline value of daily diary assessments collected after study drug administration through Week 60 (Visit 801) or early discontinuation visit will be defined as the average of the last 7 days prior to the date of the study visit and on or after the date of the previous visit. If there are less than 4 non-missing assessments in the 7-day window, the window will be extended 1 day at a time, up to 10 days, until 4 non-missing assessments are found, but the window will not be extended beyond the date of the previous visit. If at least 4 non-missing measurements are still not found, the visit will be missing. If a 7-day window is not present between visits, the postbaseline value will be the average of at least 4 non-missing assessments prior to the current visit, and on or after the previous visit. If at least 4 non-missing assessments are not available and the visit window is 5 or 6 days in length, then at least 3 non-missing assessments prior to the current visit, and on or after the previous visit will be acceptable.

### **5.2.2.1. Induction Period Considerations**

The baseline value for the safety analyses for the Induction Period is defined as the last non-missing measurement on or prior to the date of first study drug administration (expected at Week 0, Visit 2). Other definitions of baseline value, such as the last measurement on or prior to rescue, may be used to conduct additional supporting analyses.

### **5.2.2.2. Maintenance Period Considerations**

The baseline value for the safety analyses will be the last available value before the intial dose in the Maintenance period (expected at Week 16, Visit 8). Other definitions of baseline value, such as the last measurement on or prior to reassignment to active treatment, may be used to conduct additional supporting analyses.

### **5.2.3. Analysis Methods**

The main analysis of categorical efficacy variables and health outcomes variables will use a logistic regression analysis with region, baseline disease severity (IGA) and treatment group in the model. The p-value and 100(1-alpha)% CI for the odds ratio from the logistic regression model are used for primary statistical inference. The difference in percentages and 100(1-alpha)% CI of the difference in percentages using the Newcombe-Wilson without continuity

correction will be reported. The p-value from the Fisher's exact test will also be produced as a secondary analysis.

The main analysis for all continuous efficacy and health outcomes variables will use mixed model repeated measures (MMRM) analysis. The MMRM model will use a restricted maximum likelihood (REML) estimation. The model will include treatment, region, baseline disease severity, visit, and treatment-by-visit-interaction as fixed categorical effects and baseline and baseline-by-visit-interaction as fixed continuous effects. An unstructured (co)variance structure will be used to model the between- and within-patient errors. If this analysis fails to converge, the heterogeneous autoregressive [ARH(1)], followed by the heterogeneous compound symmetry (CSH), followed by the heterogeneous Toeplitz (TOEPH) will be used. The Kenward-Roger method will be used to estimate the degrees of freedom. Type III tests for the least-squares means (LSM) will be used for the statistical comparison. The LSM difference, standard error, p-value and 100(1-alpha)% CI will also be reported.

Fisher's exact test will be used for the adverse events (AEs), discontinuation, and other categorical safety data for between-treatment group comparisons. Continuous vital signs, body weight, and other continuous safety variables, including laboratory variables will be analyzed by an ANCOVA with treatment group and baseline value in the model. The significance of within-treatment group changes from baseline will be evaluated by testing whether or not the treatment group LSM changes from baseline are different from zero; the standard error for the LSM change will also be displayed. Differences in LSM will be displayed, with the p-value associated with the LSM comparison to placebo and a 95% CI on the LSM difference also provided. In addition to the LSMs for each group, the within-group p-value for the change from baseline will be displayed. Treatment-emergent high/low for categorical laboratory safety analyses will also be produced.

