Study I9N-MC-FCAB (FCAB) is a Phase 2, multicenter, randomized, double-blind, placebo-controlled, parallel-group, outpatient study evaluating the efficacy and safety of LY3375880 subcutaneous (SC) 600 mg every 4 weeks (Q4W), 150 mg Q4W, and 50 mg Q4W as compared to placebo Q4W in adult subjects with moderate-to-severe AD. In addition, LY3375880 300mg Q4W will be evaluated during the maintenance period.

The study duration will be up to 65 weeks over 4 study periods:

- Period 1: Screening Period, lasting 8 to 35 days prior to Week 0 (baseline, Visit 2).
- Period 2: Induction Period, lasting from Week 0 (baseline, Visit 2) through Week 16 (Visit 8).
- Period 3: Maintenance Period, lasting from Week 16 (Visit 8) through Week 52 (Visit 17, inclusive).
- Period 4: Post-Treatment Follow-Up Period, lasting 8 weeks from Week 52 (after Visit 17) to Week 60 (Visit 801).

Treatment Arms and Duration:

Subjects will be randomized 1:1:1:1 at Week 0 to 1 of 4 treatment groups: placebo SC Q4W, LY3375880 SC 600 mg Q4W, LY3375880 150 mg Q4W, or LY3375880 50 mg Q4W. The study duration will be up to 65 weeks (Screening Period: Up to 5 weeks; Induction Period: 16 weeks; Maintenance Period: 36 weeks; Post-Treatment Follow-up Period: 8 weeks).

Number of Subjects:

Approximately 200 subjects will be randomized.

Statistical Analysis:

Efficacy will be conducted on the intent-to-treat population. Safety analyses will be conducted on the safety population.

Treatment comparisons of discrete efficacy variables between LY3375880 and placebo will be made using a logistic regression analysis with treatment, baseline disease severity (Investigator's Global Assessment [IGA] [3 versus 4]), and geographic region in the model. Treatment comparisons of the continuous efficacy variables will be made using a mixed-effects model of repeated measures (MMRM) analysis with treatment, baseline disease severity, geographic region, visit, and treatment-by-visit interaction as fixed categorical effects and, if a baseline score is available, baseline score and baseline score-by-visit interaction as fixed continuous effects. All tests of treatment effects will be conducted at a 2-sided alpha level of 0.05, with no control for multiple comparisons.

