9.9. Medical Resource Utilization and Health Economics

Health Economics and Medical Resource Utilization parameters will not be evaluated in this study.

10. Statistical Considerations

Approximately 200 subjects will be randomized at a 1:1:1:1 ratio in the blinded induction dosing period to LY3375880 50 mg, 150 mg, 600 mg, and placebo (50 subjects per dosing regimen).

Assuming 36% and 8% of subjects achieve an IGA score of 0 or 1 (clear or almost clear skin) and ≥ 2 -point improvement from baseline at Week 16 for LY3375880 and placebo, respectively, pairwise comparisons to placebo have at least 90% power using a 2-sided Fisher's exact test at the 0.05 significance level, with no adjustment for multiple comparisons.

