10.2. Statistical Analyses

10.2.1. General Statistical Considerations

Statistical analysis of this study will be the responsibility of Lilly or its designee. A detailed SAP describing the statistical methodologies will be developed by Lilly or its designee.

Efficacy analyses will be conducted on the intent-to-treat (ITT) population. This set includes all randomized subjects, even if the subject does not take the assigned treatment, does not receive the correct treatment, or otherwise does not follow the protocol.

Safety analyses will be conducted on the safety population. This set includes all data from all randomized subjects receiving at least 1 dose of the IP according to the treatment to which the subjects were randomized.

When reported, descriptive statistics will include the number of subjects, mean, standard deviation, median, minimum, and maximum for continuous measures, and frequency counts and percentages for categorical measures.

Treatment comparisons of discrete efficacy variables between LY3375880 and placebo will be made using a logistic regression analysis with treatment, baseline disease severity (IGA 3 versus 4), geographic region, and, if applicable, baseline scores (such as baseline EASI score for a comparison of EASI-75) in the model. The percentages, difference in percentages, and 95% confidence interval (CI) of the difference in percentages will be reported. Treatment-by-region interaction will be added to the logistic regression model of the primary and key secondary

variables as a sensitivity analysis. If this interaction is significant at a 2-sided 0.1 level, further inspection will be used to assess whether the interaction is quantitative (i.e., the treatment effect is consistent in direction but not size of effect) or qualitative (the treatment is beneficial for some but not all regions).

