| Itch NRS                               | • Itch NRS score
• Change from baseline in Itch NRS score             | MMRM                            | ITT; PPS  | LY3375880 600-mg or LY3375880 150-mg or LY3375880 50-mg vs PBO; Week 16 | Exploratory Analysis |
|  | • Proportion of patients with at least a 4-point improvement in Itch NRS | Logistic regression using NRI   | ITT; PPS (those with baseline Itch NRS of 4 or greater) | LY3375880 600-mg or LY3375880 150-mg or LY3375880 50-mg vs PBO; Week 16 | Exploratory Analysis |
| Skin Pain Numeric Rating Scale (NRS)   | • Skin Pain NRS score
• Change from baseline in Skin Pain NRS score   | MMRM                            | ITT; PPS  | LY3375880 600-mg or LY3375880 150-mg or LY3375880 50-mg vs PBO; Week 16 | Exploratory Analysis |
| Patient-Oriented Eczema Measure (POEM) | • POEM score
• Change from baseline in POEM score                     | MMRM                            | ITT   | LY3375880 600-mg or LY3375880 150-mg or LY3375880 50-mg vs PBO; Week 16 | Exploratory Analysis |
| Dermatology Life Quality Index (DLQI)  | • DLQI total score
• Change from baseline in DLQI                     | MMRM                            | ITT   | LY3375880 600-mg or LY3375880 150-mg or LY3375880 50-mg vs PBO; Week 16 | Exploratory Analysis |

Abbreviations: ITT = intent-to-treat; MMRM = mixed model repeated measures; NRI = nonresponder imputation; NRS = Numeric Rating Scale; PBO = placebo; PPS = per protocol set.

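### The SAP leaves the baseline score out of the logistic model for EASI and SCORAD responders; Protocol 10.2.1 includes it, and the protocol synopsis does not

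*SAP*

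**What the plan says.** The logistic model is described in three places.

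- **Protocol 10.2.1:** treatment, IGA stratum (3 versus 4), "geographic region, and, if applicable, baseline scores (such as baseline EASI score for a comparison of EASI-75) in the model". Protocol 10.2.3.2 applies this model to EASI-50, EASI-75, EASI-90, SCORAD-75 and SCORAD-90 at Week 16.
- **Protocol synopsis, Statistical Analysis:** treatment, "baseline disease severity (Investigator's Global Assessment [IGA] [3 versus 4]), and geographic region in the model". There is no baseline score.
- **SAP 5.2.3:** a "logistic regression analysis with region, baseline disease severity (IGA) and treatment group in the model" for all categorical efficacy and health outcome variables. The odds ratio and p-value from this model carry the main inference. A Newcombe-Wilson interval for the difference and a Fisher p-value are reported alongside.

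SAP 5.3 adjusts all models for the two stratification factors and adds a baseline value only when the analysis is an MMRM. SAP Table FCAB.5.2 sends the EASI and SCORAD responders to the 5.2.3 model. It also lists an exploratory itch endpoint, "Proportion of patients with at least a 4-point improvement in Itch NRS", restricted to patients with a baseline score of 4 or more. The SAP does not mention that its logistic model is shorter than the one in Protocol 10.2.1.

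**The concern.** For EASI-75, the SAP leaves out the covariate that the protocol body names as its example. EASI-50/90 and SCORAD-75/90 are endpoints of the same kind: a threshold on percent change from a continuous baseline. One analyst working from Protocol 10.2.1 and another from SAP 5.2.3 would report different odds ratios, intervals and p-values for five secondary endpoints, and each could cite a governing document.

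Two things are at stake. The first is pre-specification: an unblinded interim look is planned when about 40% to 60% of patients have finished induction, so there should be one model per endpoint before then. The second is adjustment. With about 50 patients per arm, a two-level IGA term removes only part of any chance imbalance in a continuous severity score that the trial already collects.

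**Working it through.** **1. The plan's own power figure.** Inputs from Protocol Section 10: "Assuming 36% and 8% of subjects achieve an IGA score of 0 or 1" (LY3375880 and placebo respectively, with a 2-point improvement), "50 subjects per dosing regimen", and a claim that pairwise comparisons "have at least 90% power using a 2-sided Fisher's exact test at the 0.05 significance level".

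Power = sum over i, j of Bin(i; 50, 0.36) x Bin(j; 50, 0.08) x 1[Fisher p <= 0.05] = 91.4%.

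The claim reproduces. It rests on an unadjusted test, so the choice of covariates cannot move it.

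**2. Terms in the logistic model.**

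| Source | Treatment | IGA 3/4 | Region | Baseline score |
|---|---|---|---|---|
| Protocol 10.2.1 | yes | yes | yes | yes, if applicable |
| Protocol synopsis | yes | yes | yes | no |
| SAP 5.2.3 and 5.3 | yes | yes | yes | no (MMRM only) |

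**3. Endpoints affected.** For IGA endpoints the baseline score is IGA itself. Entry requires IGA of at least 3 on a 0 to 4 scale, so the 3-versus-4 term already carries it. That leaves three EASI and two SCORAD responder endpoints.

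**4. Chance imbalance.** The standard deviation of a difference in baseline means, in SD units, is sqrt(2/50) = 0.20. P(|difference| > 0.3 SD) = P(|Z| > 1.5) = about 13% for one dose against placebo. If the score correlates 0.6 with the IGA stratum (assumed), the part left after IGA has SD 0.20 x sqrt(1 - 0.36) = 0.16. The probability falls to P(|Z| > 1.875) = about 6%.

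**5. Effect on power.** Neither document gives EASI or SCORAD response rates, or says how strongly the baseline score predicts response. All of the following are assumptions: 50 versus 50; half of patients at IGA 4, with response odds divided by 1.5; 20% Japan; correlation 0.6 between score and IGA; odds ratio (OR) per SD of the score from 1.0 to 3.0. Each cell is 4,000 simulated trials with a Wald test for treatment, without and then with the score.

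| OR per SD | 15% vs 40% | 25% vs 50% | 8% vs 36% |
|---|---|---|---|
| 1.0 | 81.8 to 81.7 | 74.6 to 74.2 | 94.4 to 94.1 |
| 1.25 | 82.1 to 81.9 | 75.3 to 75.4 | 94.5 to 94.3 |
| 1.5 | 82.9 to 83.2 | 73.8 to 75.2 | 94.4 to 94.7 |
| 2.0 | 83.5 to 85.4 | 77.3 to 80.0 | 94.6 to 95.4 |
| 3.0 | 84.9 to 88.4 | 79.0 to 83.5 | 95.3 to 97.0 |

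The change runs from -0.4 to +4.5 points. It is within about half a point of zero up to OR 1.25, and 0.8 to 4.5 points at OR 2 to 3.

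**6. What adjustment does to the estimate.** At 15% vs 40% and OR 3.0, the median log odds ratio goes from 1.54 to 1.78 and its standard error from 0.537 to 0.599 (0.599/0.537 = 1.12). At OR 1.0 the figures are 1.40 to 1.41 and 0.506 to 0.512 (ratio 1.01). Power rises only where the estimate grows faster than its standard error.

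**7. Sparse responses.** With 8% placebo response, the chance of no placebo responder in 50 is 0.92^50 = 1.5%, or about 62 of 4,000. In the 8% vs 36% cells, 48 to 66 simulated trials gave unusable estimates and were dropped; elsewhere at most one was. If placebo response were 4% (assumed, for the strictest thresholds), 0.96^50 = 13%. An empty arm breaks the three-term model as well, so this is not caused by the added score.

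**8. Itch.** A separate simulation of the 4-point responder assumed 45 per arm and 14% vs 34%. Power went from 59.4% to 63.7% when Week 16 itch depended weakly on baseline, and moved by about 0 to 1 point otherwise.

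**The case against.** The strongest reply is that the SAP does not stand alone against the protocol. The synopsis gives exactly the SAP's three terms, so the protocol disagrees with itself and the SAP follows one of its two versions. A reader might infer that the SAP simply breaches the protocol; the synopsis rules that out. It does not settle the matter, because the body section is the more detailed one and gives a worked example that the SAP does not follow.

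The protocol's term is conditional, and Protocol 10.2.1 lets non-principal method changes go without an amendment if they are justified in the study report. Both points are true. But EASI-75 is the protocol's own case of when the condition is met, and the SAP neither flags nor justifies a change.

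Baseline severity is also partly handled already. Randomization is stratified by IGA, and every logistic model includes it. EASI and SCORAD response is scaled to the patient's own baseline. The continuous EASI and SCORAD analyses carry baseline terms, and baseline EASI is a planned subgroup for EASI-75. This stands, and it is why the expected gain is small.

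Finally, adjustment is not free. In logistic regression it changes the conditional odds ratio being estimated and raises its standard error. That stands too.

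A reader might also infer that the protocol requires baseline itch in the itch responder model. It names no such endpoint. The 4-point responder appears only in the SAP, as exploratory, and Protocol 10.2.3.3 reaches it only by a general reference to the models already described.

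**Conclusion.** The point holds as an unexplained disagreement over the inferential model for five secondary responder endpoints, with Protocol 10.2.1 on one side and the synopsis and SAP on the other. Including the score is the better choice: it follows the more specific protocol text, uses data already collected, and costs at most about 0.4 points of power in the cases examined.

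The size is small: -0.4 to +4.5 points, conditional on assumed response rates, prognostic strength and a 0.6 correlation with IGA. Gains above 2 points appear only at an odds ratio per SD of 2 or more, and nothing in the documents shows that the scores are that prognostic.

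A reader might infer that the primary result or the sample size is in doubt. Neither is: baseline IGA is in every version of the model, and the 91.4% rests on an unadjusted Fisher test. The Newcombe-Wilson differences and Fisher p-values are also unchanged.

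**What to change.** Before unblinding:

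- Amend SAP 5.2.3 and 5.3 so that the logistic model for EASI-50/75/90 includes continuous baseline EASI, and the model for SCORAD-75/90 includes continuous baseline SCORAD, alongside treatment, IGA stratum and region.
- Align the protocol synopsis with 10.2.1.
- Name a fallback for sparse or separated data, chiefly for EASI-90 and SCORAD-90. Firth-penalized logistic regression is one option; another is to rely on the Fisher p-value already planned.
- As an improvement only, add baseline Itch NRS to the exploratory 4-point itch responder model.

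If the team prefers the three-term model, it should say so in the SAP with a reason and correct Protocol 10.2.1 instead. If the assessment committee has already seen unblinded data, staff who have not should make the change and date it.

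The cost is a few sentences and no new data. The price in the analysis is a different conditional odds ratio with a somewhat larger standard error.

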### **5.5. Multicenter Studies**

This study will be conducted by multiple investigators at multiple sites internationally. The countries will be categorized into geographic regions, as described in Section 4.2.

For the analysis of the primary endpoint, treatment-by-region interaction will be added to the logistic regression model as a sensitivity analysis and results from this model will be compared to the primary model (without the interaction effect). If the treatment-by-region interaction is significant at a 2-sided  $\alpha$  level of 0.1, the nature of this interaction will be inspected as to whether it is quantitative (ie, the treatment effect is consistent in direction across all regions but not in size of treatment effect) or qualitative (the treatment is beneficial in some but not all regions). If the treatment-by-region interaction effect is found to be quantitative, results from the primary model will be presented. If the treatment-by-region interaction effect is found to be qualitative, further inspection will be used to identify in which regions LY3375880 is found to be more beneficial.

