|   | • Proportion of patients achieving IGA [0]  |                                 | Maintenance                | LY3375880 600-mg or LY3375880 300-mg or LY3375880 150-mg or LY3375880 50-mg vs PBO; Week 52 | Secondary analysis   |
|   | • Proportion of patients achieving IGA [0]  | Logistic regression using NRI   | ITT                        | LY3375880 600-mg or LY3375880 150-mg or LY3375880 50-mg vs PBO; Week 16                     | Secondary analysis   |
| Eczema Area and Severity Index (EASI)                   | • EASI score
• Change from baseline in EASI score
• Percent change from baseline in EASI score                                | MMRM                            | ITT; PPS                   | LY3375880 600-mg or LY3375880 150-mg or LY3375880 50-mg vs PBO; Week 16                     | Secondary analysis   |
|   | • Proportion of patients achieving EASI50
• Proportion of patients achieving EASI75
• Proportion of patients achieving EASI90 | Logistic regression using NRI   | ITT; PPS                   | LY3375880 600-mg or LY3375880 150-mg or LY3375880 50-mg vs PBO; Week 16                     | Secondary analysis   |
| Body Surface Area (BSA) Affected by AD                  | • BSA score
• Change from baseline in BSA score  | MMRM                            | ITT                        | LY3375880 600-mg or LY3375880 150-mg or LY3375880 50-mg vs PBO; Week 16                     | Exploratory analysis |
| SCORing Atopic Dermatitis (SCORAD)                      | • SCORAD score
• Change from baseline in SCORAD score
• Percent change from baseline in SCORAD score                          | MMRM                            | ITT                        | LY3375880 600-mg or LY3375880 150-mg or LY3375880 50-mg vs PBO; Week 16                     | Secondary analysis   |
|   | • Proportion of patients achieving SCORAD75
• Proportion of patients achieving SCORAD90  | Logistic regression using NRI   | ITT; PPS                   | LY3375880 600-mg or LY3375880 150-mg or LY3375880 50-mg vs PBO; Week 16                     | Secondary analysis   |

| Measure                                | Variable   | Analysis Method (Section 5.2.3) | Population (Section 5.2.1)                              | Comparison/Time Point   | Analysis Type        |
|--|--|---------------------------------|---|---|----------------------|

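### The designated odds-ratio inference for binary endpoints has no rule for an arm with zero responders, a realistic outcome on placebo for the strictest secondary endpoints

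*SAP*

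**What the plan says.** - **Main analysis.** SAP 5.2.3 uses a "logistic regression analysis with region, baseline disease severity (IGA) and treatment group in the model" for categorical efficacy and health outcome variables. The p-value and "CI for the odds ratio from the logistic regression model are used for primary statistical inference". The section does not say whether the p-value is Wald or likelihood-ratio, or what happens if an arm has no responders.
- **Accompanying results.** The same paragraph plans the difference in percentages and a "CI of the difference in percentages using the Newcombe-Wilson without continuity" correction. It then adds: "The p-value from the Fisher's exact test will also be produced as a secondary analysis".
- **Fallbacks.** For the MMRM, SAP 5.2.3 lists three alternative covariance structures, in order, if the model does not converge. Logistic regression has no counterpart.
- **Scope.** SAP Table FCAB.5.2 applies logistic regression with nonresponder imputation to the primary endpoint and to secondary endpoints that include IGA 0, EASI-90 and "Proportion of patients achieving SCORAD90". Under SAP 5.4.1, subjects who are rescued or permanently stop study drug count as nonresponders, which can only lower the counts.
- **Interaction model.** For the primary endpoint, SAP 5.5 states that "treatment-by-region interaction will be added to the logistic regression model as a sensitivity analysis".
- **Sample size.** Protocol Section 10 plans 50 subjects per arm, with 36% responders on active and 8% on placebo for the primary endpoint. It claims at least 90% power for a two-sided Fisher's exact test at 0.05. Neither document gives a placebo rate for IGA 0, EASI-90 or SCORAD-90.

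**The concern.** Placebo is the reference arm for all three dose comparisons. If it has no responders, the likelihood keeps rising as the placebo log-odds goes to minus infinity. The odds ratio then has no finite estimate for any dose that has responders, so one empty arm spoils all three contrasts at once. Covariates do not cure this.

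What is at stake is the result that the SAP designates as inferential. The contrast that is clearest to the eye, responders on active and none on placebo, is the one where the odds ratio and its interval stop being usable. The p-value then depends on a test type that the SAP leaves open. Someone would have to decide after unblinding which of several conflicting results to believe.

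**Working it through.** **Inputs.** From the documents: n = 50 per arm, 36% against 8% for the primary endpoint, two-sided 0.05. Assumed: placebo rates of 1% to 5% and an active rate of 16% for the strict endpoints. IGA 0 is a subset of the primary response, because every subject enters with IGA of at least 3, so its placebo rate cannot exceed the primary rate. EASI-90 and SCORAD-90 have no such bound in the documents.

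**1. The plan's own figure.** Summing the two binomial distributions over all outcomes where Fisher's p is at most 0.05 gives power of 91.4% at 36% against 8%. The stated figure of at least 90% reproduces.

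**2. Chance of an empty placebo arm.** P(0/50) = (1 − p)^50.

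| Placebo rate | 1% | 2% | 3% | 4% | 5% | 8% |
|---|---|---|---|---|---|---|
| P(0/50) | 61% | 36% | 22% | 13% | 7.7% | 1.5% |

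**3. What the model returns at 0/50.** The four-arm model (treatment, IGA stratum, region) was fitted with 0/50 on placebo and 6, 8 and 10 of 50 on the active arms. The strata were illustrative: 40% IGA 4 and 20% Japan.

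| Active | Wald p | Likelihood-ratio p | Firth profile p | Fisher p |
|---|---|---|---|---|
| 6/50 | 0.990 | 0.0031 | 0.011 | 0.027 |
| 8/50 | 0.989 | 0.00057 | 0.0023 | 0.0058 |
| 10/50 | 0.989 | 0.00010 | 0.00045 | 0.0012 |

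The fitted log odds ratios (16 to 17) and standard error (about 1256) only mark where the iterations stopped. At 18/50 against 0/50 the Wald p is still 0.989, while Fisher's is 1.2 × 10⁻⁶.

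A hand check of the 8/50 row uses the unadjusted 2×2 table, where Firth's method amounts to adding 0.5 to each cell. The odds ratio is (8.5/42.5)/(0.5/50.5) = 20.2, which is finite. The penalised log-likelihood is 8.5 ln(8.5/51) + 42.5 ln(42.5/51) + 0.5 ln(0.5/51) + 50.5 ln(50.5/51) = −25.79. With a common rate it is 9 ln(9/102) + 93 ln(93/102) = −30.44. Twice the difference is 9.30 on 1 df, p = 0.0023.

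**4. Power by exact enumeration.** Unadjusted 2×2, with Wald counted as non-significant when a cell is zero.

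| Active vs placebo | Wald | Firth | Fisher |
|---|---|---|---|
| 16% vs 1% | 20% | 85% | 70% |
| 16% vs 2% | 30% | 74% | 57% |
| 36% vs 4% (primary) | 86% | 99% | 99% |
| 36% vs 8% (primary, as planned) | 92.3% | 94.5% | 91.4% |

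For the primary endpoint at 36% active, Wald power is 93.2%, 92.8%, 90.8% and 86.2% at placebo rates of 7%, 6%, 5% and 4%.

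**5. Type I error by the same enumeration.** The unpenalised likelihood-ratio test gives 5.7%, 8.5%, 9.2% and 6.7% at null rates of 2%, 3%, 4% and 8%. Firth gives 1.3% to 4.7% over 2% to 8%. Wald gives about 0% to 1.3%.

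**6. Treatment-by-region model.** With an assumed 10 Japanese placebo subjects, P(no responders) = 0.92^10 = 43% even at the planned 8%.

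**The case against.** **The effect would not be hidden.** A reader might infer that clear effects would be lost or reported only as p near 1. The documents do not support that. The Fisher p-value and the Newcombe-Wilson interval are planned in the same paragraph, and both work with a zero cell: for 6/50 against 0/50 the interval is 2.4% to 23.8%. This stands. What remains is that the SAP ranks Fisher as secondary and does not say which result governs when it conflicts with the odds ratio.

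**The SAP does not specify a Wald test.** This also stands: p of about 0.99 is a consequence of the usual software default, not of anything written. Reading the SAP as a likelihood-ratio test does not close the gap, though. That test exceeds 5% at the null rates examined, and the interval still has no finite upper limit.

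**The primary endpoint is largely safe.** A reader might infer that the primary test loses power as soon as the placebo rate is below 8%. It does not: Wald power is slightly higher at 7% and 6% than at 8%, and drops below 90% only between 5% and 4%.

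**The rare-endpoint rates are assumed.** They are. At 16% against 5%, Wald (29.5%) and Fisher (29.3%) have the same power, so the Wald test's loss against Fisher is gone by then.

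**The consequences are contained.** The Wald test errs on the conservative side. SAP 5.6 has no multiplicity control, so a failed secondary test affects no other test. The interaction model is a sensitivity analysis. All of this limits the weight of the point but does not remove it.

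**Conclusion.** The point holds as a gap in the designated inference for strict binary secondary endpoints. Whenever placebo has no responders, the primary odds ratio is infinite and its interval unbounded under any maximum-likelihood test. At assumed placebo rates of 5% to 1% this has probability 8% to 61%. The p-value is then either uninformative (Wald) or comes from a test with type I error up to 9.2% at the null rates examined (unpenalised likelihood ratio). At an assumed 16% against 2%, power is 30% for Wald, 57% for Fisher and 74% for Firth.

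For the primary endpoint at the planned 8% the issue is minor: a 1.5% chance of an empty placebo arm and Wald power of 92%. It becomes material at about 4% or less, where Wald power is 86% against 99% for Firth.

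These conclusions rest on 50 per arm, on assumed rates for the strict endpoints, and on unadjusted 2×2 calculations for power and type I error. The four-arm fit used illustrative strata. The change is worth making before unblinding; the trial's main conclusion does not hang on it.

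**What to change.** In SAP 5.2.3, state that the binary efficacy logistic models, including the treatment-by-region sensitivity model in SAP 5.5, are fitted by Firth penalised likelihood. Take p-values and odds-ratio confidence intervals from the profile penalised likelihood. This matters: for 6/50 against 0/50 in the four-arm fit, Wald inference on the Firth estimate gives p = 0.067, against 0.011 from the profile. Keep Fisher's exact test and the Newcombe-Wilson difference as supporting results.

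The cost is one SAP sentence and one software option. The odds ratio is slightly shrunken when events are common. Power at 36% against 8% is not reduced (94.5% for Firth, 92.3% for Wald, unadjusted 2×2).

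Exact logistic regression, or a rule that Fisher governs when any arm has zero responders, would also close the gap. Letting Fisher govern uses output that is already planned, but it gives up covariate adjustment and, at the assumed rates of 16% against 1% or 2%, some power.
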